## **III. HYPOTHESES TO BE TESTED BY THE APW-RSV II TRIAL**

### **A. PRIMARY HYPOTHESES**

In infants hospitalized with RSV bronchiolitis, the addition of azithromycin therapy (compared to placebo) to routine bronchiolitis care:

1. Reduces the likelihood of developing post-RSV RW ( $\geq 3$  episodes) measured over a follow-up period of 18-48 months.
2. Modifies the airway bacterial microbiome community structure, and these changes are related to the occurrence of post-RSV RW:
  - a. More specifically, based on our preliminary data we will evaluate if azithromycin therapy results in reduction of *Moraxella* abundance and whether lower *Moraxella* abundance is associated with reduced odds to develop RW.

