### **B. SECONDARY AND EXPLORATORY HYPOTHESES:**

In infants hospitalized with RSV bronchiolitis, azithromycin therapy (compared to placebo) will result in:

1. Decreased nasal lavage levels of IL-8, neutrophil elastase, and matrix metalloproteinase-9 (MMP-9) measured on day 15 after randomization.
2. Not different rates of upper airway colonization with macrolide-resistant bacteria measured at the end of study treatments (day 15 after randomization) and at the 6-months clinic visit.
3. Not different incidence of treatment-related adverse reactions.
4. Reduced likelihood and longer time to develop 4th wheezing episode.
5. Reduced likelihood and longer time to develop physician asthma diagnosis.

6. Fewer annualized days with: a) wheezing, b) any respiratory symptoms, c) use of rescue albuterol, d) antibiotic use, e) oral corticosteroid use, f) parental absence from work and infant absence from day care, and g) nights with awakening due to respiratory symptoms.
7. Lower rates of: a) oral corticosteroid use, b) antibiotic courses, c) ED and urgent care visits, d) hospitalizations for respiratory symptoms, f) upper respiratory infections.
8. Smaller proportion of children: a) who were prescribed asthma controllers medications: ICS and/or montelukast, b) who developed RW, c) have physician asthma diagnosis.
9. Lower cumulative number of subsequent wheezing episodes.
10. Lower mean total IgE level and eosinophil counts measured at yearly follow up visits.
11. Smaller proportion of children with at least one positive specific IgE (SigE) to inhalant allergens measured at the first and last yearly follow up visit.
12. Modifications of the viral and/or the fungal components of the airway microbiome, which are related to the occurrence of post-RSV RW.

[figure not shown]

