## **F. OUTCOME VARIABLES**

### **1. PRIMARY OUTCOME MEASURES**

- a. Clinical trial outcome: The occurrence of a third episode of post-RSV wheezing measured over a follow up duration of 18-48 months, quantified by a Cox proportional hazards regression model, and compared between the groups.

*Primary outcome assessment:* Episode of wheezing will be detected by the question “Has your child’s chest sounded wheezy or whistling (with and without a cold)? This question was adopted from the International Study of Asthma and Allergies in Childhood (ISAAC) study, and was previously utilized in our pilot APW-RSV study and in the RBEL study. Data collection will be conducted in a standardized way, during study visits and phone calls, utilizing Data Collection Forms that have been modified from our APW-RSV study and in the RBEL study.

*Definition of a new distinct wheezing event vs. continuation of previous wheezing symptoms:* In order to define a new wheezing episode a child should not wheeze for at least 7 days before the new event. If the time frame from the previous wheezing episode (last time that the child wheezed) to the onset of wheezing symptoms is shorter than 7 days, these wheezing symptoms would be attributed to the previous wheezing episode and will not be counted as a new event. This approach was utilized in our previous pilot APW-RSV study.

*Time frame for primary outcome assessment:* For the purpose of this study, wheezing detected during the initial RSV bronchiolitis will not be included in the count of post-RSV wheezing. The time frame for measurement of post-RSV wheezing (and other long-term outcomes) starts at the end of the treatment period (2 weeks after randomization) and ends at end of the follow-up period. Therefore, a wheezing episode that occurs at the first 2 weeks of the study, does not “count” toward the outcome of RW.

- b. Microbiome study outcome: Upper airway microbiome community structure measured at the end of study treatments, and its relationship with the occurrence of post-RSV RW ( $\geq 3$  episodes).

See the analysis plan for details on the analytic approach of the microbiome studies.

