To examine the relationship between microbiome changes and the diagnosis of RW, we will apply a linear mixed model to bacteria of interest such as the bacteria that are significantly different between the two groups identified at individual time points, as we have previously performed. Microbiome data will be normalized to satisfy the assumption of normality by a logarithmic transformation. In the linear mixed model, transformed bacterial abundance will be modeled as the response, and the sample collection time points, treatment groups and RW outcome as fixed effects and patients as random effect. P-values from multiple comparisons will be corrected by the false discovery rate (FDR) approach.

Finally, we will perform a whole genome sequencing (WGS) on a subset of the bio-samples. Among all samples obtained at the end of study treatments, we will choose 50 samples with the strongest positive associations and 50 with the strongest negative associations with RW: these 100 samples will be selected for WGS sequencing. The library preparation, whole genome shotgun sequencing, and data processing will be performed as previously described in the Human Microbiome Project. We will characterize the microbial community structure at species the level, identify other microbial components such as viruses, and reconstruct the metabolic pathways of the bacterial community for each sample. Similar statistical strategies will be used for the WGS data as described in the 16S rRNA gene data analysis. We will be alert to any changes in data quality; if needed, we will modify methods or repeat samples to obtain rigorously validated results.

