### **B.2. Microbiome outcomes:**

We will utilize the whole study population (n=200) for this aim. This sample size provides 90% power to detect the difference for a given taxa between two groups, with effect size (5%) and standard deviation (SD1=2 and SD2=10) and alpha=0.05. However, 141 patients will be sufficient to provide 80% power to detect the same effect size. All sample size calculations assume 10% sample failed rate, which may be from different stages of the experiments,

**Figure 3.** Anticipated effect size of the intervention: proportion of patients who will not develop recurrent wheeze in the 2 treatment groups

such as patient drop out, sample preparation and sequencing failure (the combined failure rate related to the last 2 reasons in our APW-RSV trial was less than 4%). These power calculations were performed based on the assumption that we will observe half of the effect size and standard deviation detected in our preliminary data, in which *Moraxella* decreased significantly after azithromycin treatment. We used a decreased effect size to infer the sample size as *Moraxella* was a relatively high abundance taxon in the data and was affected by the intervention in our preliminary studies. In this proposal, we are also interested in comprehensive detection of the difference of relatively rare taxa in those two groups. We will be more confident to classify relatively rarely taxa in the Miseq deep sequencing platform (we anticipate 4x more reads/sample) than with the Roche 454 sequencing platform, in which our preliminary data was generated.

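### The 16S mixed model relating microbiome to recurrent wheeze (RW) has no RW-by-time term, so it estimates neither the change nor the end-of-treatment relationship; secondarily, the whole-genome subset is chosen by an undefined association with RW

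*Combined protocol and SAP*

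**What the plan says.** **The questions.** Section III.A, hypothesis 2, states that azithromycin "Modifies the airway bacterial microbiome community structure, and these changes are related to the occurrence of post-RSV RW". Section V.F.1b (and II.F.1) defines the microbiome outcome as "Upper airway microbiome community structure measured at the end of study treatments, and its relationship with the occurrence of post-RSV RW". The first concerns change; the second concerns a level at one visit.

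**The model.** Section VII.A.2 compares the arms at randomization, week 2 and month 6, and then turns to RW: "To examine the relationship between microbiome changes and the diagnosis of RW, we will apply a linear mixed model". In that model "transformed bacterial abundance will be modeled as the response, and the sample collection time points, treatment groups and RW outcome as fixed effects", with patient as a random effect and false discovery rate (FDR) correction. No interaction or change score appears. By contrast, section VII.A does name change-from-baseline contrasts for the clinical mixed models.

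**The whole-genome (WGS) subset.** From the end-of-treatment samples, "we will choose 50 samples with the strongest positive associations and 50 with the strongest negative associations with RW". The section then adds: "Similar statistical strategies will be used for the WGS data as described in the 16S rRNA gene data analysis". It names no score, taxon, model or data source that would give a single sample an association with RW, and it does not call the WGS results descriptive.

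**The concern.** A model with time, arm and RW as main effects allows one RW difference, the same at every visit. It cannot represent a difference in change, because it sets that difference to zero. Its single RW coefficient mixes a pre-treatment visit and a six-month visit with the end-of-treatment visit that defines the outcome. Two errors follow. A difference that appears only after treatment is diluted. A difference already present at randomization, with no differential change, would be flagged and could be read as a relationship with change. This model is the only test of RW that section VII.A.2 specifies for the full cohort.

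The WGS issue is narrower. 16S is the only sequencing described for all end-of-treatment samples, so it is the likely basis for the ranking, though this is not stated. If samples are picked because their 16S profile lines up with RW, a later RW test on WGS features that follow the 16S profile partly recovers the selection. FDR correction assumes valid null p-values and does not repair this.

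**Working it through.** **Inputs from the documents.** 200 children and 10% sample failure (VII.B.2), so 200 x 0.9 = 180. Three visits (VII.A.2). RW risks of 71.6% and 55.1% (VII.B.1), mean 63.35%, so about 114 with RW and 66 without. The plan gives no power or error rate for any RW test; its microbiome sample size concerns the arm comparison. The only figure to reproduce is 50 + 50 = 100 samples.

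**Assumptions, not in the documents.** RW difference 0.5 SD; total SD 1 at each visit; within-child correlation rho 0.1 to 0.5; RW share 50-60% for the averaged and week-2 figures and 63% for the change figures; complete visits.

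**Step 1: what the RW coefficient estimates.** Let d0, d2 and d6 be the RW minus non-RW differences at randomization, week 2 and month 6. The written model forces d0 = d2 = d6, and its estimate is (d0 + d2 + d6)/3.
- Week 2 only: 0.5/3 = 0.167.
- Week 2 and month 6: 1.0/3 = 0.333.
- All three visits: 0.5.

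**Step 2: power.** Let f = sqrt(1/n1 + 1/n0). The standard errors are f x sqrt((1 + 2rho)/3) for the average, f for week 2 alone, and f x sqrt(2(1 - rho)) for week 2 minus randomization. Power is approximately Phi(effect/SE - 1.96).

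Example at rho = 0.3:
- Average, 90 v 90: f = 0.149, SE = 0.149 x 0.730 = 0.109, Phi(0.167/0.109 - 1.96) = 33%.
- Week 2, 90 v 90: Phi(0.5/0.149 - 1.96) = 92%.
- Change, 114 v 66: f = 0.155, SE = 0.155 x 1.183 = 0.183, Phi(0.5/0.183 - 1.96) = 78%.

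| Where the 0.5 SD difference lies | Averaged coefficient | Week-2 level | Change, randomization to week 2 |
|---|---|---|---|
| Week 2 only | 24-42% | 90-93% | 67-90% |
| Week 2 and month 6 | 77-94% | 91-92% | 67-90% (same contrast, 0.5 - 0) |
| All three visits | 98-100% | 91-92% | 5% (no change to find) |

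The first-row ranges for the averaged and week-2 columns combine the formula with a simulation that includes an arm effect.

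**Step 3: why arm-by-time is also needed.** Arm shifts abundance at week 2 and, under the trial's hypothesis, also shifts RW. From "effect size (5%) and standard deviation (SD1=2 and SD2=10" the arm difference is 5/sqrt((2^2 + 10^2)/2) = 0.69 SD on the abundance scale. In simulation with a true week-2 RW difference of 0.5 SD, RW-by-time alone gave 0.56-0.57, while both interactions gave 0.49-0.51. With no RW difference, RW-by-time alone gave a false contrast of 0.07-0.09 SD and 6-9% false positives; with both terms the contrast was about 0, with 5-7%.

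**Step 4: WGS subset with no true association.** Assumed: 180 samples, 40 independent taxa, 16S-WGS correlation 0.5 to 0.9. The sample score is the sum over taxa of the 16S value times that taxon's RW/non-RW difference.

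| Selection rule | False positives per taxon | At least one taxon passes FDR |
|---|---|---|
| Random within RW status | 5% | 4-7% |
| Highest and lowest 50 on the score | 8-14% | 14-46% |
| Score extremes within RW status | 13-28% | 38-100% |

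At correlation 0, every rule gives 5%. Ranking on one pre-named taxon regardless of RW gives 5-6%.

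**The case against.** **The interaction may be intended.** The section refers to earlier work for its method, which cannot be checked here. That stands, and the point is therefore about what is written. If the term is intended, writing it costs nothing.

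**The power loss depends on the pattern.** This also stands. The documents do not say when an RW difference would appear, and with a constant difference the averaged coefficient beats the week-2 contrast. A reader might infer that the planned model cannot find an RW relationship. That is not supported: it does well when the difference persists or is constant. The firmer objection is that its coefficient is not the quantity that hypothesis 2 or the outcome definition names.

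**A week-2 contrast is a level, not a change.** Correct. The 90-93% answers the outcome definition. Hypothesis 2 needs the change contrast, at 67-90%. Both should be reported and kept distinct.

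**WGS circularity needs two unstated steps:** that 16S-RW results drive the ranking, and that RW is then tested in the subset. This stands in part. The stated uses of WGS are species, viruses and pathways, and the 16S strategies also include arm comparisons. The 16S mixed model cannot carry over unchanged, since WGS uses one visit per child. There is still a reason to test RW, because section III.B, item 12, proposes "Modifications of the viral and/or the fungal components of the airway microbiome, which are related to the occurrence of post-RSV RW". But that item is secondary or exploratory, section V.F.3, item q, makes viral and fungal work depend on further funding, and features unrelated to 16S show no inflation. A reader might infer that the WGS results will be false. The documents do not support that: they fix neither the ranking nor the tests, and the protocol does pre-name one taxon, *Moraxella*, for which ranking regardless of RW would be nearly harmless.

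**Conclusion.** The main point holds. As written, the mixed model assumes equal change in children with and without RW and averages three visits, so it estimates neither the change in hypothesis 2 nor the end-of-treatment relationship in the outcome definition. That follows from the listed terms and needs no assumption. The size does: 24-42% power against 90-93% (level) or 67-90% (change) applies to a 0.5 SD difference confined to week 2, and the gap narrows or reverses under other patterns.

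The WGS point is secondary and conditional. The selection rule is undefined, and one natural reading makes RW tests circular for features that track 16S. The inflation figures illustrate direction under assumptions from outside the documents; they are not properties of the plan. The full-cohort 16S analysis is not affected by the WGS selection.

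The clinical primary outcome is untouched by either point. The microbiome-RW relationship is listed among the primary outcomes in sections II.F.1 and V.F.1, although the Trial Summary calls the microbiome objective secondary. A change should be made, with medium confidence in its practical size.

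**What to change.** **Mixed model.** In section VII.A.2, write the fixed effects as time, arm, RW, RW-by-time and arm-by-time, with patient as random effect. Report the week-2 RW contrast for the end-of-treatment outcome, and the RW difference in change from randomization to week 2 for hypothesis 2. State which p-values enter the FDR correction, since there are now two RW contrasts per taxon. This is SAP wording on the same samples and data. The cost is a small loss of power if the RW difference is constant over time (91-92% against 98-100%).

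**WGS subset.** State how a sample's association with RW is scored. If selection by association is kept, report WGS-RW results as descriptive, without p-values. The cost is giving up formal WGS-RW inference. Random selection within RW status, blind to the 16S results, would keep tests valid, but it changes which samples are sequenced and gives less extreme contrasts. With 50 v 50, the SE is sqrt(2/50) = 0.2 and power for 0.5 SD is Phi(0.5/0.2 - 1.96), about 70%. It is a trade-off and not a wording change.

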## **B. SAMPLE SIZE JUSTIFICATION**

[figure not shown]
### **B.1. Clinical outcome:**

Power calculations were performed using the program Power and Precision, Version 4. They account for recruitment of patients over 3 consecutive RSV seasons (~5 months per year) with a follow up period of 18-48 months (**Figure 1: Study Design**). Our power computations are based on an evaluation of the four year survival and hazard curves generated by 190 participants of the RBEL I cohort who share the same characteristics as the controls in this proposed research, and hence used to estimate the RW rate in the control group. The survival pattern observed in our randomized pilot study (APW-RSV) was utilized to estimate the effect of the intervention. The RBEL survival curves show a low placebo group hazard rate (HR) of about 2% during the first three months after hospitalization. This HR increases steadily to about 5% per month at the end of the first year. After that, HRs decrease steadily to 3% per month by the end of year 2 to a steady monthly rate of 2% during year 3, and 1% during year 4. These assumptions yield a four-year hazard rate of 71.6%, nearly identical to the actual rate of 70.4% observed in RBEL I. We used the HR as described as the basis for the placebo group in our power computation. These projected hazard rates yield a four-year hazard rate of 55.1%. Thus, the power computations summarized below represents hazard rates of 71.6% in the placebo group and 55.1% in the azithromycin group over the follow-up period. Based on the parameters described above, two-sided tests at the 0.05 level of significance, and assuming a dropout rate of 20%, **power computations yield a requirement of 94 randomized subjects per group for a power of 0.9, and 70 per group for a power of 0.8.** Based on these considerations, we will randomize a total of up to 200 subjects or 94 per group, numbers that yield the target power of 0.9. In evaluating these computations, it is important to note that we have assumed a hazard ratio during the first 18 months of at least 2. While this is a substantial hazard ratio, we emphasize in the next paragraph that our pilot randomized trial with one year of follow-up yielded a hazard ratio of 0.34 (comparing azithromycin with placebo) meaning that the observed risk associated with placebo compared to azithromycin was nearly 3.

**We strongly believe that these power computations yield an adequate and indeed conservative sample size for the following reasons:** First the excellent target power of 0.9 and the need for only 70 subjects per group to achieve a power of 0.8 suggest that we will still have adequate power if recruitment is slower than it has been in the past. Second, the assumed HR ratios ( $55.1/71.6 = 0.77$ ) are substantially greater than the 0.34 observed in our APW-RSV pilot study. Although this large hazard rate ratio difference between those projected in this study (0.77) and the pilot study (0.34) are mitigated somewhat by the fact that the pilot study follow-up period was only one year, we have based our computations on hazard rate ratios that are closer to 1 than in the pilot study, even during the first year. Therefore, we are powered to detect between group differences that are smaller than were observed in our pilot study. Third, we assumed a HR of 1 during years 3-4. This is a very conservative approach as we believe that prevention of inflammatory damage to the airway during the acute RSV bronchiolitis will result in ongoing preventative effect for wheezing prevention during childhood

### **B.2. Microbiome outcomes:**

We will utilize the whole study population (n=200) for this aim. This sample size provides 90% power to detect the difference for a given taxa between two groups, with effect size (5%) and standard deviation (SD1=2 and SD2=10) and alpha=0.05. However, 141 patients will be sufficient to provide 80% power to detect the same effect size. All sample size calculations assume 10% sample failed rate, which may be from different stages of the experiments,

**Figure 3.** Anticipated effect size of the intervention: proportion of patients who will not develop recurrent wheeze in the 2 treatment groups

such as patient drop out, sample preparation and sequencing failure (the combined failure rate related to the last 2 reasons in our APW-RSV trial was less than 4%). These power calculations were performed based on the assumption that we will observe half of the effect size and standard deviation detected in our preliminary data, in which *Moraxella* decreased significantly after azithromycin treatment. We used a decreased effect size to infer the sample size as *Moraxella* was a relatively high abundance taxon in the data and was affected by the intervention in our preliminary studies. In this proposal, we are also interested in comprehensive detection of the difference of relatively rare taxa in those two groups. We will be more confident to classify relatively rarely taxa in the Miseq deep sequencing platform (we anticipate 4x more reads/sample) than with the Roche 454 sequencing platform, in which our preliminary data was generated.

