## **A.2. Microbiome outcomes:**

We will use the streamlined 16S analytical pipeline developed in The Genome Institute for the Human Microbiome Project to perform the microbiome analysis. Bacteria counts will be rarified to the same number across all the samples to minimize the bias potentially caused by read depth. To evaluate the effect of azithromycin treatment on the upper airway and gut microbiome, we will compare the bacterial community structure between azithromycin and placebo groups at each of the following 3 time points: randomization, week 2, and month 6, utilizing multivariate statistical testing that are widely used for 16S microbiome analysis. First, NMDS based on Bray-Curtis dissimilarity will be used to identify the microbial clustering patterns and assess the similarity between the two groups in a reduced dimensional space at two individual time points. Then, we will use PERMANOVA to test the significant differences of the overall bacterial community between the two groups. To correct for potential confounding factors, we will test individual variables in a PERMANOVA model. All the variables that show a trend towards an association with the treatment assignment ( $P < 0.15$ ) will be included in the model, as described previously. To identify the signature bacteria taxa that contribute to the difference between two compared groups, we will apply Metastats, a statistical approach developed in Human Microbiome Study for differential bacteria feature identification. P-values from multiple comparisons will be corrected by the false discovery rate (FDR) approach. Lastly, we will measure both alpha and beta diversity of the bacterial community in the two groups. Alpha diversity index such as Shannon diversity and richness to evaluate the complexity of the whole microbial community; Wilcox-sum-Rank testing will be used to test the difference of diversity between compared groups. Beta diversity represented by Bray-Curtis dissimilarity will be used to indicate the inter-subjects variation in the bacterial composition. All analysis will be performed by R (<http://www.r-project.org/>) and Bioconductor. The above analyses will allow us to characterize the microbial community at each individual sampling point, and to evaluate how it is affected by azithromycin treatment.

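### The microbiome power calculation halves the pilot effect and the pilot SD together, so it is sized for the full pilot standardised effect, for one taxon at unadjusted alpha

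*Combined protocol and SAP*

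**What the plan says.** Section VII.B.2 (Microbiome outcomes) sets the sample: "We will utilize the whole study population (n=200) for this aim". It then states "This sample size provides 90% power to detect the difference for a given taxa between two groups". For the smaller total it adds that "141 patients will be sufficient to provide 80% power to detect the same effect size". The inputs behind both of these figures are written as "with effect size (5%) and standard deviation (SD1=2 and SD2=10) and alpha=0.05". A 10% sample failure rate is built in.

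The section gives the origin of these inputs: the assumption is that "we will observe half of the effect size and standard deviation detected in our preliminary data". The next sentence begins "We used a decreased effect size to infer the sample size as". Its reasons are that *Moraxella* was an abundant taxon that responded to treatment in the pilot. The section goes on to say that less common taxa are of interest too.

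Section VII.A.2 describes a search for taxa that differ between the arms, and says "P-values from multiple comparisons will be corrected by the false discovery rate (FDR) approach". The power section makes no adjustment to alpha. *Moraxella* is singled out as a specific question in sections III.A and V.F.3 (item p).

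**The concern.** A reader takes from section VII.B.2 that the sample was sized with room to spare, since only half the pilot effect is assumed and there is still 90% power. If the SD is halved as well, that room was not created. The calculation then describes the pilot's own signal-to-noise ratio for *Moraxella*, which section II.B.2 reports as the genus that distinguished the arms at the end of treatment in a pilot of 39 sequenced children.

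The stated power is also for one taxon at 0.05, while the taxon-wise analysis is FDR-corrected. What is at stake is how a null result for a less common taxon is interpreted. Read against a stated 80% to 90% power for a reduced effect, it would look more informative than the calculation supports.

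**Working it through.** **Inputs.** From section VII.B.2: difference 5 (percentage points); SDs 2 and 10; alpha 0.05; 10% failure; N=200 or 141. From section V.A: 1:1 allocation. The section does not say whether the test is two-sided; I assume it is, as section VII.B.1 does for the clinical outcome ("two-sided tests at the 0.05 level of significance"). Evaluable per arm: 200 × 0.9 / 2 = 90, and 141 × 0.9 / 2 = 63.45.

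**Formula.** SE = √((SD1² + SD2²)/n); power = Φ(difference/SE − z), with z = 1.960 at alpha 0.05.

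**1. The plan's own figures.**

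| SDs | N=200 | N=141 |
|---|---|---|
| 2 and 10 (as printed) | SE = √(104/90) = 1.075; 5/SE = 4.651; power 99.6% | SE = √(104/63.45) = 1.280; 5/SE = 3.905; power 97.4% |
| 10 in both arms | SE = √(200/90) = 1.491; 5/SE = 3.354; power 91.8% | SE = √(200/63.45) = 1.775; 5/SE = 2.816; power 80.4% |
| Stated | 90% | 80% |

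The printed SDs do not give the stated power. With them, 90% power needs only 44 evaluable per arm, or 98 in total after 10% failure. One-sided testing, a Welch t-test and other ways of applying the failure rate do not bring the totals to 200 and 141. A common SD of 10 comes close to both pairs.

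**2. Does halving both create an allowance?** If the printed values are half the pilot values, the pilot had difference 10 and SDs 4 and 20. These are back-calculated; the documents do not give them.

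- Halved: 5/√((2² + 10²)/2) = 5/7.211 = 0.693.
- Pilot: 10/√((4² + 20²)/2) = 10/14.422 = 0.693.

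Power is identical at any N and alpha. The same cancellation holds with a common SD: 5/10 = 10/20 = 0.5.

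**3. Half the effect, pilot SDs kept (alpha 0.05).**

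| Implied pilot SDs | N=200 | N=141 |
|---|---|---|
| 4 and 20 | SE = √(416/90) = 2.150; 5/SE = 2.326; power 64% | SE = √(416/63.45) = 2.561; 5/SE = 1.953; power 50% |
| 20 in both arms | SE = √(800/90) = 2.981; 5/SE = 1.677; power 39% | SE = √(800/63.45) = 3.551; 5/SE = 1.408; power 29% |

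**4. Multiplicity.** The number of taxa is not given, so I assume m from 10 to 100 and use alpha = 0.05/m. This is the strictest FDR step, so each figure is a lower bound when several taxa truly differ. N=200, difference 5:

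| SDs | m=10 (z=2.807) | m=45 (z=3.261) | m=100 (z=3.481) |
|---|---|---|---|
| 2 and 10 | 97% | 92% | 88% |
| 10 in both arms | 71% | 54% | 45% |
| 4 and 20 (half the pilot effect) | 32% | 18% | 12% |

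The middle column is only a rough guide. It comes from the pilot comparison of arms in section II.B.2 (q/p = 0.009/0.0002 = 45) and assumes that *Moraxella* ranked first among the genera tested.

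**The case against.** **There may be spare power after all.** On the printed SDs, 90 evaluable per arm give 90% power down to a difference of (1.960 + 1.282) × 1.075 ≈ 3.5, about 70% of the pilot standardised effect. A reader might infer from the cancellation that the trial has no margin for a smaller effect. The documents do not support that on the printed inputs: there is a margin, but it comes from the mismatch between SDs and stated power, not from the halving. With a common SD of 10 the same limit is (1.960 + 1.282) × 1.491 ≈ 4.8, so almost no margin is left.

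**Perhaps only the effect was halved.** The pilot values are not printed, and the following sentence mentions only the effect. If so, the allowance is real. But the sentence puts both nouns under the word half, and would then itself need correcting.

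**Halving both may be deliberate.** For relative abundances, a taxon half as abundant may well have about half the difference and half the SD. That is a reasonable model, and keeping the full *Moraxella* SD for a rarer taxon is a choice, not an arithmetic necessity. What stands is that on this model the standardised effect was not reduced, so the smaller effect adds no caution to the power.

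**Alpha 0.05 is defensible for *Moraxella*.** That is correct, since it is pre-specified, and the section speaks of power for a given taxon. The primary microbiome outcome is community structure, which is tested by PERMANOVA. The multiplicity point therefore concerns only the taxon-wise search.

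**Conclusion.** The point holds, on the natural reading that both quantities were halved. The calculation then assumes the pilot's full standardised effect, and the reduced effect it cites gives no protection against a smaller one. The stated power also applies to a single pre-specified taxon at unadjusted alpha, not to the search across taxa.

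The size is conditional. Power for half the pilot effect at alpha 0.05 is about 64% (N=200) and 50% (N=141) if the implied pilot SDs are 4 and 20, or about 39% and 29% if the implied common pilot SD is 20. A reader might take one of these pairs, set against 90% and 80%, as the definite loss of power. The documents do not allow that, because the printed SDs do not produce the printed power and the pilot SDs are not stated. Nor do they support a single FDR-adjusted figure, because the number of taxa is not given.

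Nothing here calls the sample size into question. Appendix 2 records that 200 children were recruited.

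**What to change.** In section VII.B.2:

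1. Reconcile the SDs with the printed power first, and say which SDs were used and whether the test is two-sided.
2. State the pilot difference and SDs.
3. Say that the calculation assumes the full pilot standardised effect for one pre-specified taxon at unadjusted alpha 0.05, and delete the sentence that begins "We used a decreased effect size to infer the sample size as" as a justification. Alternatively, recompute with the effect halved and the pilot SDs kept.
4. Report power for half the pilot effect as depending on the SD choice: about 64% and 50%, or about 39% and 29%, at N=200 and 141, until step 1 settles it.
5. If a multiplicity-adjusted figure is given, give a range over an assumed number of taxa (for example 32% down to 12% at N=200 for 10 to 100 taxa with SDs 4 and 20), labelled as a lower bound for FDR.

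The cost is one rewritten paragraph and a look at the pilot data. The number of children, the samples and the analysis methods stay as they are. The stated power for smaller effects becomes less favourable.
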